10.4.5.2 Secondary Efficacy Analyses

Secondary efficacy endpoints include the following:

- Participant-level PPV on Day 0 and on Day 1;
- Participant-level DR on Day 0 and on Day 1;
- Participant-level FPR on Day 0 and on Day 1;
- Region-level FPR on Day 0 and on Day 1;
- Participant-level discrepant PET negative rate between Day 0 and Day 1;
- Participant-level TNR on Day 0 and on Day 1;
- Region-level TNR on Day 0 and on Day 1.

Secondary efficacy endpoints will be analyzed on the FAS. Point estimates and 2-sided 95% exact binomial CIs will be presented for each central reviewer separately.

10.4.5.3 Exploratory Efficacy Analyses

The exploratory efficacy endpoints include the following:

- Proportion of participants with any change in intended PC treatment due to either the Day 0 or Day 1 scan;
- Composite CDR, PPV and DR of the Day 0 and Day 1 scan;

- CDR, participant- and region-level PPV and DR of the Day 0 and/or Day 1 scan as a function of baseline variables;
- Relationship between PET-positivity (biodistribution measures such as SUVs and lesion-to-background ratio), versus true/false positivity and as a function of lesion location and size;
- Difference in the number of lesions detected per participant on the Day 0 versus the Day 1 scan;
- Lesion-level overall agreement rate on the Day 0 and Day 1 scans, on the Day 0 and reference scans, and on the Day 1 and reference scans;
- PSA over time and change from baseline;
- PSA velocity and PSA doubling time (PSADT) at the end of the study and at baseline.

Binary exploratory endpoints will be summarized with points estimates and corresponding 2-sided 95% exact binomial CIs based on the FAS.

Difference in the number of lesions detected per participant on the Day 0 versus the Day 1 scan will be summarized descriptively and compared using a paired *t*-test. Other exploratory endpoints including PSA value at each scheduled time point and change from baseline, PSA velocity, and PSADT will be summarized using descriptive statistics.

Descriptive statistics, graphical methods, and statistical modeling as appropriate may be used to explore the relationship between PET-positivity (biodistribution measures such as SUVs and lesion-to-background ratio) and true/false positivity.

In addition, CDR, PPV and DR will also be assessed as a function of the following baseline variables:

- PSA at baseline prior to the scan (<0.5, 0.5 <1.0, 1.0 <2.0, 2.0 <5.0, ≥5);
- PSADT;
- PSA velocity;
- Testosterone at baseline;
- SUV mean and max;
- Lesion-to-background ratio;
- Initial Treatment Received.

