10 STATISTICAL METHODS

10.1 General Considerations

A Statistical Analysis Plan (SAP) will be written after finalizing the protocol and prior to database lock. The SAP will detail the implementation of all the planned statistical analysis in accordance with the principal features stated in the protocol. Any deviations from the SAP will be presented in the final clinical study report.

Continuous variables will be summarized by the number of subjects, mean, standard deviation, standard error of the mean, median, 25th quartile, 75th quartile, minimum, and maximum values.

Categorical variables will be summarized using frequency counts and percentages.

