#### 7.0 STATISTICAL METHODS

#### 7.1 General Considerations

#### 7.1.1 Standard Calculations

- Variables requiring calculation will be derived using the following formulas:
- Baseline: A baseline value, unless specified otherwise, is the last non-missing value recorded prior to the Cu-SAR-bisPSMA administration. If an assessment has both a date and time that exactly match the date and time of first dose of study drug, the assessment will be counted as baseline. For participants who are enrolled, but not dosed, the last assessment collected on or prior to the enrollment date is considered baseline.
- Change from Baseline: Change from baseline will be calculated for each patient at the specified time point as the value at the specified time point minus the baseline value.
- Study Day: The day of Cu-SAR-bisPSMA administration will be on Day 0 as specified in the study protocol schedule of events, but for Clinical Data Interchange Standards Consortium (CDISC) compliance, the study day variables will consider this as "Day 1" as there cannot be a Day 0. Study listings will be presented as "Day 0" to match the protocol.
- For a given date, study day is calculated in the SDTM data as days since the date of single dose of Cu-SAR-bisPSMA:
  - Study day = date dose date + 1, where date  $\geq$  dose date
  - Study day = date dose date, where date < dose date
- For a given date, study day is calculated in the TLF presentations as days since the date of single dose of Cu-SAR-bisPSMA:
  - Study day = date dose date, where date  $\geq$  dose date
  - Study day = date dose date, where date < dose date
- Days: Durations, expressed in days, between one date (date1) and another later date (date2) are calculated according to the following formula: duration in days = (date2 date1 + 1).

September 4, 2024 CONFIDENTIAL Page 16 of 46

■ Body Mass Index (BMI): BMI  $(kg/m^2)$  = weight  $(kg) / [[height (cm)/100]^2]$ .

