## 7.2 General Comments on the Statistical Analyses

- Age will be computed from the informed consent date and the date of birth.
- Continuous variables will be summarized using number (n), mean, standard deviation (SD), median, 25th quartile, 75th quartile, minimum, and maximum.
- Categorical data will be reported with frequency counts and percentages.
- All relevant data captured on the electronic case report forms (eCRFs) and from external laboratories including specific descriptions of 'other' and comments fields will be provided in by-participant listings. All listings will be sorted by participant number and visit in ascending order.
- If a clinical laboratory result is reported relative to a lower/upper range of detection for an assay, for example, "<10", the numeric portion of the result (10) will be used for statistical analyses and the full result, including any symbols, will be provided in the patient listings.
- Analysis Data Model (ADaM) datasets will be prepared using CDISC ADaM Version 2.1 or later, and CDISC ADaM Implementation Guide Version 1.1 or later. Pinnacle 21 Community Validator Version 3.1.2 or later will be utilized to ensure compliance with CDISC standards.
- Version 9.4 (or higher) of the SAS® statistical software package will be used to provide all tables, listings, and figures.
- The analyses described in this plan are considered a priori, in that they have been defined prior to the first patient enrolled. Any changes to the planned analyses after first patient enrolled will be documented in this SAP and in the CSR.

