## 7.6 Calculation of PSA Doubling Time and PSA Velocity

The following values of PSA are collecting for this study:

- PSA at Initial Diagnosis
- Nadir PSA after initial definitive treatment
- Most Recent PSA prior to screening #1 and #2
- Screening PSA
- PSA taken during the study at day 90 and 180 (if appliable) or after start of salvage focal therapy (can vary)

PSA doubling time (PSADT) and PSA velocity will be calculated at baseline and during the study and require different definitions. PSA at initial diagnosis will not be used for any calculations of PSA velocity or PSADT.

For calculation of PSADT and PSA velocity at **Baseline**, which will be calculated for all participants:

- PSA Velocity = Slope of the line of best fit using all available data within 12 months prior to screening as well as screening value (excluding at initial diagnosis).
- PSADT = ln(2) / ((ln(PSA value at screening) ln(oldest PSA value within 12 months prior to screening)) / (# of months from oldest PSA value within 12 months prior to PSA at screening))

September 4, 2024 CONFIDENTIAL Page 18 of 46

For calculation of PSADT and PSA velocity for on-study measurements, only the last measure of PSA taken during the study will be used. The following calculations will be done for PSA measurements **Post-Baseline**:

- PSA Velocity = Slope of the line of best fit using all available data on-study, including screening value.
  - o If the participant initiated radiation therapy on-study, the last PSA value is instead the last PSA value PRIOR to initiating radiation therapy.
- PSADT = ln(2) / ((ln(Last on-study PSA value) ln(PSA at screening)) / (# of months from last on-study PSA value to PSA at screening))
  - o If the participant initiated radiation therapy on-study, the last PSA value is instead the last PSA value PRIOR to initiating radiation therapy.
- If a participant has no post-screening value prior to initiation of radiation therapy, they will be excluded from post-baseline calculations of PSADT and PSA velocity.

For the calculation of the line of best fit for PSA Velocity, the following equations will be used for each participant, where  $x_i$  is the date of the measurement in months from screening (screening is x = 0) for each value,  $y_i$  is the PSA value, and n is the total number of datapoints for the participant for that calculation:

$$\overline{X} = \frac{\sum_{i=1}^{n} x_i}{n} \quad \overline{Y} = \frac{\sum_{i=1}^{n} y_i}{n}$$

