#### 9.14.3.6 PSA Measures Change from Baseline

Total PSA, PSA velocity, and PSADT levels will be summarized descriptively at each timepoint including a change from baseline. Boxplots showing the mean, median, Q1, Q3, and outliers for each PSA measure will be presented for each timepoint to investigate PSA over time.

Additional summaries of total PSA, PSA velocity, and PSADT levels will be presented for the following subgroups:

- Participants who received salvage focal therapy
- Participants who were TP for the primary analysis at the participant-level
- Participants who were FP for the primary analysis at the participant-level
- Participants who were TN for the primary analysis at the participant-level

All PSA, PSA velocity, and PSADT levels will be listed.

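### SAP 9.14.3.6 averages and differences raw PSA doubling time, a reciprocal that becomes huge or negative when PSA is flat or falling; its mean and mean change are uninformative and can have the wrong sign

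*Protocol*

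**What the plan says.** Protocol 10.4.5.3 lists among the exploratory endpoints "PSA velocity and PSA doubling time (PSADT) at the end of the study and at baseline", and says that "PSA velocity, and PSADT will be summarized using descriptive statistics". It takes no change in PSADT; its change from baseline belongs to the PSA value. Protocol 10.1 sets the default: "Continuous variables will be summarized by the number of subjects, mean, standard deviation, standard error of the mean, median", then quartiles and range.

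The SAP supplies the rest:

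- **Formula (7.6).** Baseline PSADT begins "PSADT = ln(2) / ((ln(PSA value at screening" and uses the oldest PSA in the 12 months before screening. The on-study version begins "PSADT = ln(2) / ((ln(Last on-study PSA value" and uses the screening PSA. Each is ln 2 divided by a difference of two logs per month.
- **Summary (9.14.3.6).** "Total PSA, PSA velocity, and PSADT levels will be summarized descriptively at each timepoint including a change from baseline". Boxplots that include the mean are planned, as are summaries for the TP, FP, TN and salvage-focal-therapy subgroups.
- **Change (7.1.1).** Taken "as the value at the specified time point minus the baseline value", a raw difference.
- **Statistics (7.2).** "Continuous variables will be summarized using number (n), mean, standard deviation (SD), median", with quartiles, minimum and maximum.

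Neither document says what to do when the log slope is zero or negative, and neither offers another scale or a cap. The one post-baseline restriction in SAP 7.6 removes PSA values after the start of radiation therapy.

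**The concern.** PSADT is the reciprocal of a slope. When the slope passes through zero, PSADT jumps from a very large positive number to a very large negative one. Two things follow. A single man with near-flat PSA can dominate the mean and SD. The ordering also breaks: a man whose PSA falls has a negative PSADT, which sorts below a man whose PSA doubles every month. A negative change in PSADT should mean faster growth, but here it also arises when growth stops.

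The design makes such values plausible. On-study spans are about 3 months, or about 6 for those who return at Day 180. Entry PSA after prostatectomy can be as low as 0.2 ng/mL, so a difference of 0.01 ng/mL can decide the sign. PSA after non-radiation focal therapy is not cut off by SAP 7.6, so a response to it would enter as a negative doubling time. At stake is a report of faster doubling in a group whose PSA growth slowed.

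**Working it through.** No sample size, power or error rate in the documents uses PSADT, so there is no plan figure to reproduce.

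**1. The SAP formula for near-flat PSA.** PSADT = ln 2 / [(ln PSA2 - ln PSA1) / months]. The PSA pairs are illustrative.

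- 1.00 to 1.01 over 3 months: ln 2 / (ln 1.01 / 3) = +209.0 months.
- 1.00 to 0.99 over 3 months: ln 2 / (ln 0.99 / 3) = -206.9 months.
- 1.00 to 1.01 or 0.99 over 6 months: +418.0 or -413.8 months.
- 0.50 to 0.51 or 0.49 over 3 months: +105.0 or -102.9 months.
- Unchanged PSA: division by zero, so no value.

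A man who moves from +10 to -207 months has a change of -207 - 10 = -217 months, although his PSA has stopped rising.

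**2. Ten men, each with baseline PSADT 6 months, followed for 6 months.** The rate is 1/PSADT, in doublings per month.

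| On study | Mean PSADT | Mean change | Median change | Change in mean rate |
|---|---|---|---|---|
| 9 unchanged, one 1.00 to 0.99 | (9×6 - 413.8)/10 = -36.0 | -42.0 | 0 | -0.017 |
| 9 unchanged, one 1.00 to 1.01 | (9×6 + 418.0)/10 = 47.2 | +41.2 | 0 | -0.016 |
| 9 worsen to 3 months, one 1.00 to 1.01 | (9×3 + 418.0)/10 = 44.5 | +38.5 | -3.0 | +0.134 |
| All 10 turn from doubling to halving in 6 months | -6.0 | -12.0 | -12.0 | -0.333 |

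In rows 1 and 2 one man swings the mean change by over 80 months on a 0.02 ng/mL difference, while the median change stays at 0. In row 3 the mean change is wrong and the median change right. In row 4 both are wrong. The rate is right in every row.

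**3. Simulation.** The documents give no PSA distribution or measurement error, so every setting is an assumption: 40 men; true baseline PSADT with median 9 months and log SD 0.6; baseline span 9 months; true growth halved on study in every man; PSA CV 5, 10 or 15%; on-study span 3 or 6 months; one screening PSA shared by both slopes; 20,000 trials per setting. Repeat runs differ by about one percentage point.

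- *Mean change in PSADT, wrong sign:* 57% of trials at CV 10% and 3 months (90% range -88 to +80 months); 38% at CV 10% and 6 months; 16% to 66% over the six settings.
- *Median change in PSADT, wrong sign:*

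| CV | 3 months | 6 months |
|---|---|---|
| 5% | under 0.01% | 0% |
| 10% | 19% | 0% |
| 15% | 79% | 2% |

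- *Median on-study PSADT at CV 10%:* 9.5 months (3-month span) or 14.1 months (6-month span), against a true 18.
- *Share of negative on-study PSADT:* 2% to 28%.
- *Mean change in log growth rate, wrong sign:* at most 0.05% of trials. ln 2 divided by the median rate gave 15.4 to 17.4 months.

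**The case against.** The strongest reply is that the plan never relies on the mean alone. SAP 7.2 also requires the median, quartiles, minimum and maximum. SAP 9.14.3.6 adds boxplots with outliers, a listing of every PSADT, and PSA velocity at the same timepoints and in the same subgroups. Velocity is a fitted slope: finite when PSA is flat, negative when it falls. A reader who saw a mean PSADT of -36 months would suspect an artefact. This stands in part. One might infer that one or two flat PSA series drive the whole planned summary; they drive the mean and SD, not the median. The median fails only when many slopes are negative, as in the two weak cells above and the last row of the ten-man table.

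A second reply is that halved growth is an invented effect. The agent is a single diagnostic dose, and on-study PSADT excludes PSA after radiation. This also stands: the wrong-sign rates are illustrations under stated assumptions, not forecasts for this trial. The arithmetic in step 1 does not depend on them.

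Third, a reader might infer that the Protocol itself differences PSADT. It does not; the change from baseline is an SAP item. Nor does anything here reach the trial's conclusions: SAP 4.1 plans no formal hypothesis testing, and no decision uses change in PSADT.

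**Conclusion.** The concern holds for the mean, SD and change from baseline of raw PSADT in SAP 9.14.3.6. These come from a reciprocal of a slope that can be zero or negative, with no rule for either case. They are uninformative, and the mean change can have the wrong sign: in 16-66% of simulated trials under the assumed CV, spans and halved growth. The median change is usually right, but it is not a safeguard when falling or noisy PSA is common over a 3-month span. That much follows from the formula; the percentages rest on the assumptions listed.

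The consequence is limited to an exploratory descriptive endpoint. Primary and secondary results, power and error rates are untouched. It is still worth correcting, because the planned table could suggest faster doubling where growth slowed, and the remedy uses data already collected.

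**What to change.** In SAP 9.14.3.6:

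- Derive k = ln(PSA2/PSA1)/months from the same PSA pairs as SAP 7.6. It equals ln 2/PSADT, is zero for an unchanged PSA and negative for a falling one.
- Summarise k, take its change from baseline, and draw the boxplots on k, overall and in the planned subgroups.
- Report doubling time at baseline and end of study as ln 2 divided by the median k, worded as *not doubling* when the median k is zero or below. This still answers Protocol 10.4.5.3.
- Drop the mean, SD and change from baseline of raw PSADT. Keep the individual listing, with men at k ≤ 0 marked *not doubling*.
- Record the departure from the Protocol 10.1 default statistics in SAP 8.0.

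A smaller alternative is a separate stable-or-declining class with emphasis on the median. It removes undefined values but leaves no usable change from baseline for men in that class.

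The cost is a one-line derivation and SAP wording, by SAP amendment if before database lock. No new data are needed. The downside is a less familiar unit, which the back-transform largely recovers.

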10.4.6 Intra- and Inter-reader Reliability Assessments

A subset of each central reader's ⁶⁴Cu-SAR-bisPSMA PET/CT scans will be evaluated twice to assess the reproducibility of the readings and consistency among readers.

The intra-reader variability of each reader will be assessed by calculating percent agreement (concordance) and Cohen's pairwise kappa statistics along with the 95% CIs for the dichotomous results for all participants with two scan interpretations.

For inter-reader variability, the agreement among the three independent readers will be assessed by calculating percent pairwise concordance and Fleiss's overall multi-assessor kappa statistics and its 95% CIs.

10.4.7 Biodistribution Analysis

Biodistribution measures of ⁶⁴Cu-SAR-bisPSMA including, maximum and mean SUVs in lesions, visceral/soft tissues, bone, and lesion-to-background ratios will be summarized descriptively for the Biodistribution Analysis Set.

10.5 Interim Analysis

There are no interim analysis planned for this study.

10.6 Handling of Missing Data

Exploratory sensitivity analyses of the primary endpoints will be performed using participants who had non-evaluable composite Reference Standard data. Additional sensitivity analyses based on all participant in the FAS using the worst case imputation method and tipping point analysis will also be performed to examine the impact of missing or unevaluable composite Reference Standard data. These methods are described in detail in Section 10.4.5.1.

11 STUDY ADMINISTRATION AND RESPONSABILITIES

11.1 General Investigator Responsibilities

The Investigator must ensure that:

- He or she will personally conduct or supervise the study;
- His or her staff and all persons who assist in the conduct of the study clearly understand their responsibilities and have their names included in the protocol specific Study Personnel Responsibility/Signature Log;
- The study is conducted according to the protocol and all applicable regulations;
- The protection of each participant's rights and welfare is maintained;
- Signed and dated informed consent and, when applicable, permission to use protected health information are obtained from each participant before conducting study procedures. If a participant withdraws permission to use protected health information, the Investigator will obtain a written request from the participant and will ensure that no further data will be collected from the participant;
- The consent process is conducted in compliance with all applicable regulations and privacy acts;
- The IRB complies with applicable regulations and conducts initial and ongoing reviews and approvals of the study;
- Any amendment to the protocol is submitted promptly to the IRB;
- Any significant protocol deviations are reported to the Medical Monitor, the Sponsor, and the IRB according to the guidelines at each study site;
- Electronic case report form pages are completed within 5 days of each participant's visit (unless required earlier for SAE reporting);
- All SAEs and pregnancies are reported to the Sponsor or designee within 24 hours of knowledge and to the IRB per IRB requirements;
- All safety reports are submitted promptly to the IRB, as per IRB requirements.

11.2 Protocol Compliance

The Investigator is responsible for ensuring the study is conducted in accordance with the procedures and evaluations described in this protocol.

11.3 Compliance with Ethical and Regulatory Guidelines

The Investigator will ensure that this study is conducted in accordance with International Conference on Harmonization of Technical Requirements for Registration of Pharmaceuticals for Human Use, or with the laws and regulations of the country in which the research is conducted, whichever affords the greater protection to the study participant. For studies conducted under a USA Investigational New Drug (IND) application, the Investigator will ensure adherence to the basic principles of GCP as outlined in 21 Code of Federal Regulations (CFR) 312, subpart D, "Responsibilities of Sponsors and Investigators"; 21 CFR, Part 50, 1998; and 21 CFR, Part 56, 1998.

This study is also subject to and will be conducted in accordance with 21 CFR, Part 320, 1993, "Retention of Bioavailability and Bioequivalence Testing Samples."

Because this is a "covered" clinical study, the Investigator will ensure adherence to 21 CFR, Part 54, 1998; a covered clinical study is any "study of a drug or device in humans submitted in a marketing application or reclassification petition subject to this part that the applicant or FDA relies on to establish that the product is effective (including studies that show equivalence to an effective product) or that make a significant contribution to the demonstration of safety." This requires that Investigators and all sub-Investigators must provide documentation of their financial interest or arrangements with the Sponsor, or proprietary interests in the drug being studied. This documentation must be provided before participation of the Investigator and any sub Investigator in the study. The Investigator or sub Investigator agrees to notify the Sponsor of any change in reportable financial interests during the study and for 1 year following completion of the study. Study completion is defined as the date that the last participant has completed the protocol-defined activities.

